## Progression Free Survival:

TTET01	
Output ID: t_tte_PFS_*
 

● Analysis Population: Intent-to-Treat Patients, excluding patients without histologically confirmed BCC. Outputs will be repeated for different population combinations - please see the LoPO for details of these combinations, and the Efficacy Population section for details on populations.

● Column Variables: Disease Status (Locally Advanced, Metastatic)

● Column Totals: Totals of non-missing Disease Status

● Analysis Variables: Progression Free Survival in Months

● Statistics and Calculation Methods: Use proc freq and proc lifetest.

○ <math>\alpha</math> level for CIs is 2-sided 5%.

○ Use proc lifetest to obtain time to event (Median, Percentiles) information. The 95% confidence interval for the median is calculated using the Brookmeyer & Crowley method.

○ Range, 25th and 75th Percentiles are displayed.

● Numeric Precision and Formatting of Statistics: Use standard display in the mockup

--------	--

### Programming Note:

- Progression-Free Survival is defined as the interval between the date of first treatment and the date of Progressive Disease or Death.
- Patients without disease progression or death will be censored at the date of last tumour assessment.
- N would be the number of patients with a measurable or non-measurable disease at baseline and histologically confirmed BCC.
- Percentages are based on N.
- Patients with a measurable or non-measurable disease at baseline and histologically confirmed BCC are included in the analysis.

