5.3.4 Safety Follow-Up Phase Assessments

Patients who discontinue from the study will be asked to return to the clinic for a safety follow-up assessment 1 month, 3 months, 6 months, 9 months, and 12 months after the last dose of vismodegib (+/- 5 days), as provided by this phase II, safety study protocol,

or upon initiation of new non-permitted anti-cancer therapy. The assessments will include:

- Hematology (including hemoglobin, hematocrit, red blood cell count, full white blood cell count including differential, platelet count, and ANC) as clinically indicated
- Biochemistry (including glucose, sodium, potassium, chloride, bicarbonate, BUN, creatinine, creatine kinase [also known as creatine phosphokinase], total bilirubin, alkaline phosphatase, AST, and ALT) as clinically indicated
- Follow up for disease progression
- Concomitant therapy and new anti-cancer therapy
- AEs (including SAEs)
- For women of childbearing potential:
 - Record date of last menses
 - Assess amenorrhea/irregular menses that develops while on study:
 1. At start of amenorrhea/irregular menses, perform serum hormone evaluation at study site, including FSH, LH, E2, and TSH, and refer to gynecologist or appropriate specialist for assessment of ovaries and uterus, including ultrasound
 2. At resolution of amenorrhea/irregular menses, perform serum hormone evaluation at site, including FSH, LH, E2, and TSH. Refer to gynecologist or appropriate specialist for follow-up ultrasound ONLY if there was abnormality identified during previous ultrasound
 3. If amenorrhea/irregular menses recurs, repeat evaluations at start of recurrence as detailed previously
- Patients with metastatic BCC (newly enrolled after approval of the Study Protocol, version 4.0) will complete the M.D. Anderson Symptom Inventory (see Section 5.6 and Appendix 6), prior to having any other assessments performed at the visits
- In selected sites, patients will have blood draws for adverse event–related PK testing if any adverse events that were reported to be related to vismodegib treatment continue to be present at least 6 months after the last dose of vismodegib. Blood samples for the adverse event-related PK testing will be collected at the 6, 9, and 12 months Safety Follow-Up Visits. Blood samples for all time points will be collected even if the adverse event resolves after the 6 months Safety Follow-Up Visit.

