Scheduling of Tumor Assessments

The majority of patients in this study have locally advanced BCC, and in this disease setting measurable tumors are accessible to evaluation by physical examination.

Tumor assessment by physical examination should be performed within a maximum of 7 days prior to the first dose of study drug (baseline reading). If tumor assessment requires imaging, baseline CT/MRI scans should be performed within a maximum of 28 days prior to the first dose of study drug (on Cycle 1, Day 1). Non-measurable disease should be assessed within 28 days prior to study initiation.

Post-baseline measurable tumors accessible to evaluation by physical examination are to be performed every 4 to 8 weeks (± 5 days). For tumor assessment requiring imaging and if the baseline scans demonstrate evidence of disease, CT and/or MRI scans should occur every 8 to 16 weeks (± 5 days) or as per institutional standards. The same imaging technique must be used for a patient throughout the study.

In metastatic BCC patients who are newly enrolled after approval of the Study Protocol, version 4.0, imaging at baseline (CT and/or MRI scan) should be performed within a maximum of 28 days before first dose. Follow-up imaging studies (CT and/or MRI scan) should be performed every 8 weeks (± 5 days) from the time of the first dose, regardless of dosing delays. The same imaging technique (CT or MRI) should be used for each patient throughout the study.

If there is suspicion of disease progression based on clinical or laboratory findings before the next scheduled assessment, an unscheduled assessment should be performed.

All tumor assessments after baseline will be done within ± 5 days of the scheduled visit. If a patient inadvertently misses a prescribed tumor evaluation or a technical error prevents the evaluation, the patient may continue treatment until the next scheduled assessment, unless signs of clinical progression are present.

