8.2.1 Types of Analyses

8.2.1.1 Efficacy Analysis

The efficacy summaries will be presented for the ITT population, which will include all patients enrolled in the study.

The efficacy variable of primary interest for this study is the overall response rate (ORR), as assessed by the Investigator according to RECIST, v1.1. The summary will be

performed on patients with measurable disease at baseline. The best overall response rate (BORR) will be reported. BORR is defined as the number of patients whose best objective response is CR or PR divided by the total number of treated patients in the group for which the BORR is estimated.

Duration of response is the key secondary efficacy variable. It is defined only for the patients whose confirmed best response is CR or PR as the time interval between the date of the earliest qualifying response and the date of PD or death for any cause. For patients who are alive without progression following the qualifying response, duration of response will be censored on the date of last evaluable tumor assessment or last follow-up for progression of disease. This will be done based on Investigator's assessments.

Time to response is defined as the interval between the date of first treatment and the date of first documentation of confirmed CR or PR (whichever occur first). This will be done based on Investigator's assessments.

Progression Free Survival (PFS) is defined as the time interval between the date of the first therapy and the date of progression or death for any causes, whichever occurs first. A patient who died without a reported progression will be considered as an event on the date of death. Patients who have neither progressed nor died will be censored on the date of last evaluable tumor assessment. This will be done based on Investigator's assessments. Patients with non-measurable disease will be assessed for disease progression and included in this summary.

Overall survival (OS) is defined as the time from the date of first treatment to the date of death, regardless of the cause of death. For patients who are alive at the time of analysis, OS time will be censored at the last date the patient was known to be alive. Patients with no post baseline information will be censored at the time of first treatment with vismodegib.

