2.4.2 Missing assessments and non-evaluable designation

When no imaging/measurement is conducted all at a particular time point, the patient is not evaluable at that time point. If only a subset of lesion measurements are made at an assessment, usually the case is also considered not evaluable at that time point, unless a convincing argument can be made that the contribution of the individual missing lesion(s) would not change the assigned time point response. This would be most likely to happen in the case of PD.

For example, if a patient had a baseline sum of 50 mm with three measured lesions and during the study only two lesions were assessed, but those gave a sum of 80 mm, the patient will have achieved PD status, regardless of the contribution of the missing lesion.

If one or more target lesions were not assessed either because the scan was not done, or could not be assessed because of poor image quality or obstructed view, the Response for Target Lesions should be “Unable to Assess” since the patient is not evaluable. Similarly, if one or more non-target lesions are indicated as ‘not assessed’, the response for non-target lesions should be “Unable to Assess” (except where there is clear progression). Overall response would be “Unable to Assess” if either the target response or the non-target response is “Unable to Assess” (except where this is clear evidence of progression) as this equates with the case being not evaluable at that time point.

Appendix 1 New Response Evaluation Criteria in Solid Tumors, Version 1.1: Modified Excerpt from Original Publication with Supplementary Explanations (1) (cont.)

Best response determination in trials where confirmation of complete or PR IS NOT required:

Best response is defined as the best response across all time points (for example, a patient who has SD at first assessment, PR at second assessment, and PD on last assessment has a best overall response of PR). When SD is believed to be best response, it must also meet the protocol specified minimum time from baseline. If the minimum time is not met when SD is otherwise the best time point response, the patient's best response depends on the subsequent assessments. For example, a patient who has SD at first assessment, PD at second and does not meet minimum duration for SD, will have a best response of PD. The same patient lost to follow-up after the first SD assessment would be considered not evaluable.

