- Best Overall Response would be Stable Disease (SD) if subject's best overall response is not CR or PR, and there is at least one response assessment of CR, PR or SD with minimum of 51 days after First Dose Date without any Progressive Disease (PD) in between.
- Best Overall Response would be Progression Disease (PD) if subject's best overall response is not CR, PR, or SD, and if there is at least one response assessment of PD.
- Best Overall Response would be Not Evaluable (NE) if subject's best overall response is not CR, PR, SD, or PD, and there is at least one response assessment of NE.
- BOR would be PD if PD occurred before satisfying any of the above criteria of Best Overall Response.
- Patients who achieve best overall response of CR or PR are considered a responder.
- Best overall response rate is defined as the number of patients with a CR or PR observed at two consecutive assessments  $\geq 4$  weeks apart ( $\geq 23$  days) divided by the total number of patients with histologically confirmed measurable disease at baseline.
- N in column headings is the number of patients with a measurable or non-measurable disease at baseline and histologically confirmed BCC. Percentages are calculated based on the number of patients with a measurable disease at baseline and histologically confirmed BCC.
- Display only Responder and 95%CI for Best Overall Response Rate.

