### Programming Note:

- Duration of response will be calculated only for patients whose confirmed best response is CR or PR.
- Duration of response is the interval between the Date of First Response and the Date of Progressive Disease or Death, and is calculated only for patients with confirmed best response of CR or PR at two consecutive assessments  $\geq 23$  days.
- Patients without Progression of Disease or Death will be censored at the date of last tumour assessment and the duration of response is calculated using the interval between Date of First Response and the date of last tumour assessment.
- N would be the number of patients with a measurable or non-measurable disease at baseline and histologically confirmed BCC.
- Percentages are based on the number of patients with a measurable disease at baseline and histologically confirmed BCC, and who had a CR or PR.
- Duration of response will be calculated in Months.

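### The SAP censors PFS at the last tumour assessment, not the last evaluable one, so trailing NE visits can only hold or raise the curve; its duration-of-response rule matches neither protocol option

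*SAP*

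**What the plan says.** **PFS.** Protocol Section 8.2.1.1: "Patients who have neither progressed nor died will be censored on the date of last evaluable tumor assessment". SAP, Progression Free Survival and the matching Kaplan-Meier plot: "Patients without disease progression or death will be censored at the date of last tumour assessment". The SAP text does not restore the word evaluable anywhere.

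**Duration of response.** For responders who are alive and progression-free, Protocol Section 8.2.1.1 says "duration of response will be censored on the date of last evaluable tumor assessment or last follow-up for progression of disease". SAP, Duration of Response: "Patients without Progression of Disease or Death will be censored at the date of last tumour assessment"; the Kaplan-Meier plot specification has the same rule. Protocol Section 8.2.1.1 makes duration of response the key secondary efficacy variable.

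**NE visits.** The SAP's best-response rules assign NE when no better category applies and "there is at least one response assessment of NE". They also allow an NE assessment between two confirming assessments. The mock Target Lesion Assessment listing shows dated visits with result NE and blank diameters. Protocol Appendix 1, Section 2.4.2 adds: "When no imaging/measurement is conducted all at a particular time point, the patient is not evaluable at that time point".

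**Follow-up after the last dose.** Protocol Section 5.3.4 lists "Follow up for disease progression" at the visits 1, 3, 6, 9 and 12 months after the last dose. Table 1 schedules no tumour assessment at those visits.

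**The concern.** An NE result neither shows progression nor rules it out. If the last visits of an event-free patient are NE, the protocol stops that patient's PFS clock at the last visit that could be scored. The SAP lets it run to the last NE visit. The extra time is credited as progression-free although progression status was not established, and the credit works in one direction only, in the drug's favour.

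The extreme case is a patient whose post-baseline assessments are all NE. Best response is then NE, yet the SAP credits progression-free time up to the last of those visits. The protocol gives no PFS date for this patient either, because its provision for patients with no post-baseline information covers overall survival only.

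For duration of response the two documents give different instructions for the key secondary efficacy variable, and the protocol's own instruction offers two dates without saying which applies.

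**Working it through.** The plan gives no expected PFS or duration-of-response figure to reproduce. Its only precision figure, the 95% interval for 120/1200 adverse events, reproduces as 8.36% to 11.84% (stated 8.4% to 11.8%) and has no bearing here.

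**1. Which visits matter.** Only NE visits after the last evaluable one, in a patient with neither progression nor death. An NE visit followed by an evaluable visit, progression or death leaves the patient's date unchanged.

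**2. Shift for one patient.** Shift = number of trailing NE visits × visit interval. Physical examination is every 4 to 8 weeks; for imaging, "CT and/or MRI scans should occur every 8 to 16 weeks". Example: last evaluable visit on day 225, NE on days 281 and 337, then off study. The protocol date is day 225 and the SAP date day 337: 2 × 56 = 112 days.

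**3. Direction for PFS.** The Kaplan-Meier estimate is S(t) = ∏(1 − d_j/n_j) over event times up to t. Events d_j are the same under both rules. Moving a censoring date from c_P to a later c_S adds one to n_j at every event time with c_P < t_j ≤ c_S. Since 1 − d/(n+1) ≥ 1 − d/n, every factor is equal or larger, and so is S(t).

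**4. Size for PFS.** The documents give no count of trailing NE visits, so this is a simulation on assumptions, with 200,000 patients per scenario:
- progression exponential with median 9.5 months, borrowed from the locally advanced cohort of the earlier pivotal phase II trial (Protocol Section 1.1.2.2) and detected at the next visit;
- drop-out exponential with median 12 months, capped at 36 months (assumed);
- visits every 8 or 16 weeks, ±5 days;
- 0% to 20% of event-free patients ending on one or two NE visits (assumed).

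| Visits | Event-free patients ending on NE | 12-month PFS, protocol | 12-month PFS, SAP | Difference (points) | Median, protocol / SAP (months) |
|---|---|---|---|---|---|
| 8 weeks | 0% | 42.69% | 42.69% | 0 | 9.33 / 9.33 |
| 8 weeks | 5%, one visit | 42.70% | 42.87% | 0.17 | 9.33 / 9.34 |
| 8 weeks | 10%, one visit | 42.40% | 42.73% | 0.33 | 9.32 / 9.34 |
| 8 weeks | 20%, one visit | 42.21% | 42.85% | 0.64 | 9.31 / 9.34 |
| 8 weeks | 20%, two visits | 41.80% | 42.94% | 1.14 | 9.29 / 9.34 |
| 16 weeks | 0% | 41.12% | 41.12% | 0 | 11.00 / 11.00 |
| 16 weeks | 5%, one visit | 40.66% | 40.93% | 0.27 | 11.00 / 11.00 |
| 16 weeks | 10%, one visit | 40.47% | 41.02% | 0.55 | 10.99 / 11.01 |
| 16 weeks | 20%, one visit | 39.76% | 40.85% | 1.09 | 10.98 / 11.00 |
| 16 weeks | 20%, two visits | 39.37% | 41.18% | 1.81 | 10.97 / 11.01 |

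Each row is a separate draw, so the valid comparison is across a row.

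**5. Duration of response, three rules.** Assumptions: progression exponential with median 7.6 months (same earlier trial); last dose without progression exponential with median 8 months; 8-weekly visits on treatment; 0 to 5 follow-up visits completed, equally likely. Progression found at a follow-up visit is an event under every rule; only the censoring date differs.

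| Event-free patients ending on one NE visit | Last evaluable assessment | SAP, last assessment | Last follow-up for progression |
|---|---|---|---|
| 0%: 12-month rate; median (months) | 28.3%; 7.36 | 28.3%; 7.36 | 35.8%; 8.73 |
| 10% | 28.0%; 7.36 | 28.2%; 7.36 | 35.7%; 8.78 |
| 20% | 27.9%; 7.36 | 28.4%; 7.36 | 35.9%; 8.90 |

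The SAP lies 0 to 0.5 points above the first protocol alternative. It lies 7.5 points below the second at 12 months, with a median 1.4 to 1.5 months shorter.

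**The case against.** **Progression can be judged at some visits with missing lesions.** Appendix 1 lets progression be declared from the lesions that were measured, and any new lesion is progression. A time point with no measurement at all might not count as a tumour assessment in the SAP's sense. Both points stand. They narrow the problem to visits recorded as NE, where progression was neither shown nor excluded, and the SAP does not say whether those dates count.

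**No trailing NE visit is shown.** In the mock Target Lesion Assessment listing the NE visits come first and are followed by PR and CR, so that patient's date is the same under both rules. A reader might take the listing as evidence that the problem occurs. It shows only that NE visits are dated records.

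**The handling may sit elsewhere.** The SAP places other derivation detail, such as visit windows and the data cut, in a separate specification that is not available here. NE dates may be excluded there. That is a reason to state the rule in the SAP, not evidence that it is stated.

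**Little hangs on it.** The study is single-arm and descriptive with no hypothesis test, PFS is secondary, and the SAP's PFS table reports medians, quartiles and range rather than 12-month rates. This stands and limits the importance of the PFS part.

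**Conclusion.** The PFS mismatch is certain from the text. So is its direction under a literal reading: PFS is equal to or higher than under the protocol definition. The size is unknown. On the assumed shares it is about 0.2 to 1.8 points at 12 months with a median shift of 0.05 month or less, and it is zero if no event-free patient ends on an NE visit. These figures depend on assumed event, drop-out and NE rates and are illustrative only.

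A reader might infer that the SAP inflates duration of response as well. The documents do not support that. The protocol's second alternative, last follow-up for progression, can fall months after the last tumour assessment, and against that date the SAP would lower the curve. What can be said is that the SAP matches neither alternative and that the sign of the difference depends on which one is intended. In the simulation the choice between alternatives matters far more than the NE question. Nor does the protocol require a last-evaluable rule for duration of response, since it leaves both dates open.

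**What to change.** 1. In the SAP's PFS table and plot notes, censor at the last tumour assessment with an overall response other than NE, on or before data cut-off.
2. State the PFS date for patients with no evaluable post-baseline assessment, for example the date of first treatment.
3. Report how many censored patients end on an NE visit. The SAP's populated shells carry a 16 March 2015 clinical cut-off, so the count should be obtainable from data in hand.
4. For duration of response, choose one of the protocol's two dates and align the table note, the plot note and the protocol. If last follow-up for progression is chosen, define which record supplies that date.

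The cost is one programming condition for PFS, a few lines of text, and a PFS estimate that may be slightly less favourable. The duration-of-response item needs a decision first; its effect on the estimate depends on that choice.

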## Overall Survival:

TTET01	
Output ID: t_tte_OS_*
 

● Analysis Population: Intent-to-Treat Patients, excluding patients without histologically confirmed BCC. Outputs will be repeated for different population combinations - please see the LoPO for details of these combinations, and the Efficacy Population section for details on populations.

● Column Variables: Disease Status (Locally Advanced, Metastatic)

● Column Totals: Totals of non-missing Disease Status

● Analysis Variables: Overall Survival in Months

● Statistics and Calculation Methods: Use proc freq and proc lifetest.

○ <math>\alpha</math> level for CIs is 2-sided 5%.

○ Use proc lifetest to obtain time to event (Median, Percentiles) information. The 95% confidence interval for the median is calculated using the Brookmeyer & Crowley method.

○ Range, 25th and 75th Percentiles are displayed.

● Numeric Precision and Formatting of Statistics: Use standard display in the mockup

---------------	--

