In metastatic BCC patients (who are on study after approval of the Study Protocol, version 4.0), evidence of tumor progression prior to enrollment on study and reasons for treatment discontinuation of prior therapies will be summarized. Analysis of data regarding evidence of progression prior to enrollment and reasons for treatment discontinuation of prior therapies will be performed in metastatic BCC patients.

Efficacy Analyses:

ORR, assessed by the Investigator according to RECIST, v1.1, will be summarized. The summary will be performed on patients with measureable disease at baseline. The best overall response rates (complete and partial responders), together with the corresponding 95% Pearson-Clopper confidence intervals, will be presented.

Duration of response will be defined only for patients whose confirmed best response is complete response (CR) or partial response (PR) and will describe the time interval between the date of the earliest qualifying response and the date of progressive disease (PD) or death for any cause.

Time to response will be defined as the interval between the date of first treatment and the date of first documentation of confirmed CR or PR (whichever occur first).

PFS will be defined as the time interval between the date of the first therapy and the date of progression or death for any causes, whichever occurs first. Patients with non-measurable disease will be assessed for disease progression and included in this summary.

OS will be defined as the time from the date of first treatment to the date of death, regardless of the cause of death. Estimates for the survival function and corresponding 95% confidence interval for the time-to-event endpoints, PFS, OS, time to response, and duration of response using Kaplan-Meier estimates will be displayed by tables and graphs.

Quality of Life

The effects of skin disease on patient's quality of life will be accessed by the Skindex-16 questionnaire. Distribution of scores, mean scores, and changes from baseline for each domain, symptoms, emotions and function will be summarized over time by summary tables, line graphs with associated 95% confidence intervals, and box plots.

Disease Symptoms

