The best ORRs (confirmed complete and confirmed partial responders) together with the corresponding 95% Pearson-Clopper confidence intervals will be presented. A listing of tumor assessments and best overall response will also be presented.

Estimates for the survivor function for the time-to-event endpoints, including PFS, OS, time to response, and duration of response, will be displayed graphically using Kaplan-Meier (KM) curves. Estimates for the median time to event and the corresponding two-sided 95% confidence interval will be presented with the estimates for the other quartiles and the associated ranges (minimum, maximum). The estimates and KM curves will be presented for the ITT population.

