## Deaths:

### Summary of Deaths:

STREAM Template	Description
N/A	
Output ID: t_dd_*
 

● Analysis Populations: Safety
 
● Column Variables: Disease Status (Locally Advanced, Metastatic)
 
● Column Totals: Totals of non-missing Disease Status
 
● Analysis Variables: Number of Patients Died, Primary Reason for Death
 
● Statistics and Calculation Methods: Use proc freq for events or proc sql for patient counts.
 
● Numeric Precision and Formatting of Statistics: Use DST01 standard template in the mockup
 
● Optional Subsetting: Primary Reason for Death: Adverse Event, Disease Progression, Other.

Summary of Deaths, Population : Safety-Evaluable Patients  
Protocol: M025616  
Snapshot Date: 03 August 2015. Clinical Cut-Off Date: 16 March 2015.  
File: t\_dd\_SE.

Status	Locally Advanced (N=1119)	Metastatic (N=96)	Total (N=1215)
Number of Patients who Died	92 (8.2%)	18 (18.8%)	110 (9.1%)
Primary Reason for Death	92 (8.2%)	18 (18.8%)	110 (9.1%)
Adverse Event	65 (5.8%)	6 (6.3%)	71 (5.8%)
Disease Progression	15 (1.3%)	12 (12.5%)	27 (2.2%)
Other	12 (1.1%)	0	12 (1.0%)

Program: /opt/BIOSTAT/prod/cdpt3616/mo25616/t\_dd.sas  
Output: /opt/BIOSTAT/prod/cdpt3616/i25616f/reports/t\_dd\_SE.out  
10SEP2015 19:09

Page 1 of 1

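### The overall survival outputs specify no survival-rate estimate with a confidence interval, and at the printed death counts the median is unlikely to be reached in locally advanced disease

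*SAP*

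**What the plan says.** OS is a secondary variable (Protocol 2.2 and 8.1.2). For t_tte_OS_*, the SAP's Overall Survival section says "Use proc lifetest to obtain time to event (Median, Percentiles) information". It continues: "The 95% confidence interval for the median is calculated using the Brookmeyer & Crowley method". The range is added, and "25 th and 75 th Percentiles are displayed". Event percentages are based on N. The layout follows a standard mockup that is not reproduced. No survival probability at a fixed time is listed.

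The KM plot g_rs_km_OS_IT shows curves by disease status with censoring marks and numbers at risk. It sets a two-sided 5% level but names no CI.

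The protocol describes OS reporting in two ways. Section 8.2.1.1 shows survivor-function estimates as curves and adds: "Estimates for the median time to event and the corresponding two-sided 95% confidence interval will be presented with the estimates for the other quartiles". The SAP follows this. The Synopsis (Efficacy Analyses) asks for more: "Estimates for the survival function and corresponding 95% confidence interval for the time-to-event endpoints", to appear in both tables and graphs.

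The SAP's Summary of Deaths shell is already filled. Its row "Number of Patients who Died" gives 92 of 1119 locally advanced, 18 of 96 metastatic and 110 of 1215 in total, with a clinical cut-off of 16 March 2015.

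**The concern.** A KM median exists only if the curve falls to 50%, and the 25th percentile of survival time only if it falls to 75%. With about 8% of the locally advanced cohort dead, the curve may not reach the first level and may not reach the second. That cohort is 1119/1215 = 92% of patients.

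The only CI specified belongs to the median. Where the curve stays above 50%, that interval has no upper limit, and at best a lower limit can be printed. What remains is a range made up mostly of censored times and a crude percentage of deaths. The crude percentage ignores censoring, although planned follow-up after treatment differs between patients: 1 month under protocol versions 1 and 2, 12 months from version 3 (SAP, Disposition). The report could then carry no OS estimate with stated precision for most of the trial, although the data would support one and the Synopsis promises it.

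**Working it through.** **The plan's figures.** 92/1119 = 8.22%, 18/96 = 18.75% and 110/1215 = 9.05%. All agree with the SAP.

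**Exponential check.** A crude death proportion is not one minus KM survival, so follow-up is needed. The documents do not state it, and mean follow-up of 9 to 24 months is assumed. Hazard h = deaths / (N × mean follow-up); time to 75% survival = ln(4/3)/h; median = ln 2/h.

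- Locally advanced, 9 months: h = 92/(1119 × 9) = 0.00914 per month; 75% point 31.5 months, median 76 months.
- Locally advanced, 24 months: h = 0.00343; 84 and 202 months.
- Metastatic, 9 months: h = 18/(96 × 9) = 0.0208; 13.8 and 33 months.
- Metastatic, 24 months: h = 0.00781; 36.8 and 89 months.

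Accrual was planned over about 3.5 years (Protocol 3.2), or 42 months. On this scale the locally advanced median lies well beyond any plausible observation time, and the metastatic median is borderline at best.

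**KM simulation.** The hazard is set so that the expected death proportion equals 8.2% or 18.8%. Administrative follow-up is uniform from 3 to 42 (or 48) months, combined with exponential loss of mean 12, 18 or 24 months, or none. Mean follow-up then runs from about 9 to 25.5 months. There were 600 replicates for locally advanced and 3000 for metastatic. Each cell gives the 42-month / 48-month result. Half-widths are for 12-month survival (Greenwood, 95%), in percentage points.

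| Mean loss time | LA reaches 75% | LA reaches 50% | LA half-width | Met. reaches 75% | Met. reaches 50% | Met. half-width |
|---|---|---|---|---|---|---|
| 12 months | 75% / 79% | 5.0% / 7.7% | 2.6 / 2.5 | 97% / 97% | 54% / 55% | 12.1 / 11.9 |
| 18 months | 50% / 62% | 2.2% / 1.8% | 2.1 / 2.0 | 96% / 96% | 43% / 48% | 10.1 / 9.8 |
| 24 months | 32% / 41% | 1.0% / 0.8% | 1.9 / 1.8 | 95% / 96% | 36% / 39% | 9.1 / 8.8 |
| none | 0.3% / 0.7% | 0.2% / 0.2% | 1.3 / 1.2 | 78% / 78% | 4.5% / 4.7% | 6.4 / 6.0 |

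The 0.2% entries are single replicates (1/600). The 25% survival level is reached in under 2% of locally advanced replicates and in 0.4% to 17.5% of metastatic ones. Shorter follow-up makes the quantiles easier to reach because a higher hazard is then needed to produce the same number of deaths.

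**A second model.** This one assumes 42-month uniform accrual, cut-off at 48 months, median treatment of 9.7 months, hazard doubled after stopping, and follow-up after last dose of 1 month in 25% of patients and 12 months in the rest. The locally advanced median is reached in about 1% of replicates and the metastatic median in about 24%. The locally advanced 75% point is reached in about 19% to 23%, with a median of 12 patients at risk. The metastatic 75% point is reached in 88%, at about 22 months with about 20 at risk. Metastatic 24-month survival has a half-width of about 12 points with about 16 at risk. If deaths doubled, the locally advanced median would still be reached in only about 6% of replicates.

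**The case against.** A reader might infer that the OS table cannot deliver its quantiles and that the endpoint is left with almost no usable estimate. The documents do not support that. The metastatic 25th percentile is probably reached under every assumption tried, the metastatic median is possible, and the locally advanced 25th percentile ranges from 0.3% to 79% depending on follow-up. Event counts and percentages are also planned. Survival at any time can be read from the planned KM curve, which shows numbers at risk.

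Other points stand as limits on the argument:

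- The counts are a March 2015 snapshot of the safety population. The OS table excludes patients without histologically confirmed disease, and the final analysis (Protocol 8.1) comes later and may have more deaths.
- Actual follow-up is unknown, and the SAP's list of death sources includes a survival follow-up page. The 9.7 months in the second model comes from the earlier pivotal trial's locally advanced cohort, and the doubled hazard has no source in the documents.
- The table mockup is not shown, so it may already print survival rates. The 5% level set for the plot may have been meant for a confidence band, since no hypothesis test is planned (Protocol 8.2).
- Comparison with earlier data is a weak argument. The protocol quotes metastatic survival mainly as a median of 8 to 14 months, with a 5-year rate near 10%, and gives no 12- or 24-month rate.
- This is a single-arm safety study. Reporting a median as not estimable is honest, and the SAP's statistics match Protocol 8.2.1.1.

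None of this supplies a survival estimate with a CI in the specified text, and the Synopsis promises one.

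**Conclusion.** The point holds as a reporting gap. At the printed counts, the locally advanced median is unlikely to be reached (about 0.2% to 8% of simulations), so the only CI specified would very probably lack at least its upper limit for 92% of patients. The metastatic median is uncertain (about 5% to 55%), while the metastatic 25th percentile is probably reached (78% to 97%).

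The same data would give 12-month survival with half-widths of about 1 to 3 points in locally advanced and 6 to 12 points in metastatic disease. These figures rest on exponential survival, assumed follow-up and the March 2015 death counts. The gap between the Synopsis and the specified outputs rests on the text alone. The consequence is limited to how one secondary endpoint is reported, but the remedy is cheap enough to be worth making.

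**What to change.** In t_tte_OS_*, add the KM survival probability at 12 and 24 months, with number at risk and 95% CI (Greenwood variance, log-log scale), by disease status and in total. Show the CI on g_rs_km_OS_IT. Keep the median and quartiles where they are reached. Add a note that metastatic estimates will be imprecise, especially at 24 months, where the half-width is about 12 points under the second model and would be wider with heavier loss to follow-up.

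This brings the OS outputs into line with the Synopsis. The cost is one TIMELIST option in PROC LIFETEST, a few table rows and a band on the plot, with no new data. If the standard mockup already prints these rates, it is enough to say so in the OS table specification.
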